9.0 TREATMENT/INTERVENTION PLAN

9.1 Intervention

This is a single-arm, phase II study with a Simon minimax design testing the combination of durvalumab and tremelimumab in patients with non-TCC of the urothelial tract.

Patients will receive durvalumab 1500 mg and tremelimumab 75 mg IV Q4W for up to 4 doses/cycles, then durvalumab 1500 mg Q4W starting 4 weeks after the last combination treatment for up to 9 doses. The rationale for this dosing schedule is explained in section 3.3.

9.2 Duration of treatment, treatment beyond progression, and criteria for retreatment

Patients will continue study treatment until lack of clinical benefit, development of unacceptable toxicity, or completion of planned study treatment. Patients may be treated beyond RECIST progression if the investigator deems them to be continuing to derive clinical benefit and if they meet all of the following criteria:

- Absence of symptoms and signs (including worsening of laboratory values [e.g. new or worsening hypercalcemia]) indicating unequivocal progression of disease
- No decline in ECOG performance status from baseline
- Absence of tumor growth at critical anatomic sites (e.g. leptomeningeal disease) that cannot be managed by protocol-allowed medical interventions
- Evidence of clinical benefit (defined as the stabilization or improvement of disease-related symptoms) as assessed by the investigator.

Patients for whom radiographic disease progression is confirmed at subsequent tumor assessments may be considered for continued study treatment at the discretion of the investigator if they continue to meet the criteria above and have evidence of clinical benefit. Other immunotherapy studies have demonstrated that patients who initially derive clinical benefit from treatment and have progression while off treatment can derive clinical benefit again if they are retreated (40,46,47). Retreatment is allowed (once only) for patients meeting the retreatment criteria below. The same treatment guidelines followed during the initial 12-month treatment period will be followed during the retreatment period, including the same dose and frequency of treatments and the same schedule of assessments.

Patients may undergo retreatment in 2 clinical scenarios, described below:

- Patients who achieve and maintain disease control (i.e., CR, PR, or SD) up until the end of the treatment period may restart treatment with durvalumab 1500 mg and tremelimumab 75 mg IV Q4W for up to 4 doses/cycles, then durvalumab 1500 mg Q4W beginning 4 weeks after the last dose of combination therapy for up to 9 doses of durvalumab monotherapy upon evidence of PD (with or without confirmation according to RECIST 1.1) during follow-up provided the study is still on-going. If patients experienced unacceptable toxicity with the combination, they may resume durvalumab 1500 mg Q4W alone.
- Patients who complete the 4 dosing cycles of the combination durvalumab plus tremelimumab with clinical benefit per Investigator judgment but subsequently have evidence of PD during the durvalumab monotherapy portion, with or without confirmation according to RECIST 1.1, may restart treatment with the durvalumab dosing at 1500 mg Q4W with 75 mg of tremelimumab Q4W for 4 doses each followed by durvalumab monotherapy 1500mg Q4W (for 9 additional doses) at the investigator's discretion.

For patients who restart combination durvalumab + tremelimumab treatment, before restarting their assigned treatment, the Investigator should ensure that the patient:

- a. Does not have any significant, unacceptable, or irreversible toxicities that indicate continuing treatment will not further benefit the patient
- b. Still fulfills the eligibility criteria for this study, including re-consenting to restart durvalumab and tremelimumab and excluding previous treatment with durvalumab and tremelimumab.
- c. Has not received an intervening systemic anticancer therapy after their assigned treatment discontinuation.
- d. Has had a baseline tumor assessment within 28 days of restarting their assigned treatment; all further scans should occur with the same frequency as during the initial 13 cycles of treatment until study treatment is stopped (maximum of 13 cycles of further treatment).

During the retreatment period, patients receiving durvalumab + tremelimumab may resume durvalumab dosing at 1500 mg Q4W with 75 mg of tremelimumab Q4W for 4 doses each. Patients will then continue with durvalumab monotherapy at 1500 mg Q4W beginning 4 weeks after the last dose of combination therapy for up to 9 doses of durvalumab monotherapy.

Treatment through progression is at the Investigator's discretion, and the Investigator should ensure that patients do not have any significant, unacceptable, or irreversible toxicities that indicate that continuing treatment will not further benefit the patient.

Patients must resign the informed consent form to be treated through progression.

Patients who the Investigator determines may not continue treatment will enter follow-up.

9.3 Concomitant Treatment

Patients must inform the treating investigator about any medication taken from the time of screening until the end of the clinical phase of the study (final study visit). Any concomitant medication(s), including herbal preparations, taken during the study will be recorded.

Restricted, prohibited, and permitted concomitant medications are described in the following tables.

Permitted concomitant medications

Investigators may prescribe concomitant medications or treatments (e.g., acetaminophen, diphenhydramine) deemed necessary to provide adequate prophylactic or supportive care except for those medications identified as "excluded" as listed in the section below.

Local therapy (palliative radiotherapy, surgery, radiofrequency ablation) is allowed.

Excluded Concomitant Medications

The following medications are considered exclusionary during the study.

- Any investigational anticancer therapy (other than the protocol specified therapies)
- Any concurrent chemotherapy, radiotherapy (except palliative radiotherapy), immunotherapy, biologic or hormonal therapy for cancer treatment. Concurrent use of hormones for noncancer-related conditions (e.g., insulin for diabetes and hormone replacement therapy) is acceptable. NOTE: Treatment of isolated lesions for palliative intent is acceptable (e.g., by local surgery or radiotherapy).
- Immunosuppressive medications including, but not limited to systemic corticosteroids at doses exceeding 10 mg/day of prednisone or equivalent, methotrexate, azathioprine, and TNF- α blockers, except when required to treat investigational product-related AEs. Use of immunosuppressive medications for the management of investigational product-related AEs or in subjects with contrast allergies is acceptable. In addition, use of inhaled and intranasal corticosteroids is permitted. A temporary period of steroids will be allowed for different indications, at the discretion of the principal investigator (e.g., chronic obstructive pulmonary disease, radiation, nausea, etc).
- Live attenuated vaccines within 30 days of durvalumab and tremelimumab dosing (i.e., 30 days prior to the first dose, during treatment with durvalumab and tremelimumab for 30 days post discontinuation of durvalumab and tremelimumab) are not permitted. Inactivated vaccines, such as the injectable influenza vaccine, are permitted.

Table 7. Prohibited and Rescue Medications

Prohibited medication/class of drug:	Usage:
Additional investigational anticancer therapy concurrent with those under investigation in this study	Should not be given whilst the patient is on investigational protocol (IP) treatment
mAbs against CTLA-4, PD-1, or PD-L1	Should not be given whilst the patient is on IP treatment through 90 days after the last dose of IP.
Any concurrent chemotherapy, biologic therapy, or hormonal therapy for cancer treatment. Local therapy (palliative radiotherapy, surgery, radiofrequency ablation) is allowed.	Should not be given whilst the patient is on IP treatment. (Concurrent use of hormones for non-cancer-related conditions [e.g., insulin for diabetes and hormone replacement therapy] is acceptable.)

Prohibited medication/class of drug:	Usage:
Immunosuppressive medications, including, but not limited to, systemic corticosteroids at doses exceeding 10 mg/day of prednisone or its equivalent, methotrexate, azathioprine, and tumor necrosis factor α blockers. Herbal and natural remedies which may have immune-modulating effects should not be given concomitantly unless agreed by the sponsor.	Should not be given whilst the patient is on IP treatment. Use of immunosuppressive medications for the management of IP-related AEs or in patients with contrast allergies is acceptable. In addition, use of inhaled, topical, and intranasal corticosteroids is permitted.
Live attenuated vaccines	Should not be given through 30 days after the last dose of IP during the study

Rescue/supportive medication/class of drug:	Usage:
Concomitant medications or treatments (e.g., acetaminophen or diphenhydramine) deemed necessary by the Investigator to provide adequate prophylactic or supportive care, except for those medications identified as "prohibited" as listed above	To be administered as prescribed by the Investigator
Best supportive care (including antibiotics, nutritional support, growth factor support, correction of metabolic disorders, optimal symptom control, and pain management [including palliative radiotherapy, etc])	Should be used when necessary for all patients

Rescue/supportive medication/class of drug:	Usage:
Best supportive care (including antibiotics, nutritional support, growth factor support, correction of metabolic disorders, optimal symptom control, and pain management [including palliative radiotherapy, etc])	Should be used when necessary for all patients

Blood donation

Subjects should not donate blood while participating in this study, or for at least 90 days following the last infusion of durvalumab or tremelimumab.

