Bone lesions: Bone scan, positron emission tomography (PET) scan, or plain films are not considered adequate imaging techniques to measure bone lesions. However, these techniques can be used to confirm the presence or disappearance of bone lesions.

- Lytic bone lesions or mixed lytic-blastic lesions, with identifiable soft tissue components, that can be evaluated by cross-sectional imaging techniques such as CT or MRI can be considered measurable lesions if the soft tissue component meets the definition of measurability described above.
- Blastic bone lesions are non-measurable.

Cystic lesions: Lesions that meet the criteria for radiographically defined simple cysts should not be considered malignant lesions (neither measurable nor non-measurable) since they are, by definition, simple cysts.

- Cystic lesions thought to represent cystic metastases can be considered measurable lesions if they meet the definition of measurability described above. However, if non-cystic lesions are present in the same patient, these are preferred for selection as target lesions.

Lesions with prior local treatment: Tumor lesions situated in a previously irradiated area, or in an area subjected to other loco-regional therapy, are usually not considered measurable unless there has been demonstrated progression in the lesion. Study protocols should detail the conditions under which such lesions would be considered measurable.

II. Target Lesions: Specifications by Methods of Measurements

A. Measurement of Lesions

All measurements should be recorded in metric notation, using calipers if clinically assessed. All baseline evaluations should be performed as close as possible to the treatment start and never more than 4 weeks before the beginning of the treatment.

B. Method of Assessment

The same method of assessment and the same technique should be used to characterize each identified and reported lesion at baseline and during study. Imaging-based evaluation should always be the preferred option.

Clinical Lesions. Clinical lesions will only be considered measurable when they are superficial and ≥ 10 mm in diameter as assessed using calipers (e.g., skin nodules). For the case of skin lesions, documentation by color photography, including a ruler to estimate the size of the lesion, is suggested.

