- **Complete response (CR):** disappearance of all target lesions. Any pathological lymph nodes (whether target or non-target) must have reduction in short axis to < 10 mm.
- **Partial response (PR):** at least a 30% decrease in the sum of diameters of target lesions, taking as reference the baseline sum of diameters
- **Progressive disease (PD):** at least a 20% increase in the sum of diameters of target lesions, taking as reference the smallest sum on study (nadir), including baseline

In addition to the relative increase of 20%, the sum must also demonstrate an absolute increase of at least 5 mm.

The appearance of one or more new lesions is also considered progression.

Stable disease (SD): neither sufficient shrinkage to qualify for PR nor sufficient increase to qualify for PD, taking as reference the smallest sum on study.

B. Special Notes on the Assessment of Target Lesions

Lymph Nodes. Lymph nodes identified as target lesions should always have the actual short axis measurement recorded (measured in the same anatomical plane as the baseline examination), even if the nodes regress to <10 mm on study. This means that when lymph nodes are included as target lesions, the sum of lesions may not be zero even if CR criteria are met since a normal lymph node is defined as having a short axis <10 mm.

Target Lesions That Become Too Small to Measure. While on study, all lesions (nodal and non-nodal) recorded at baseline should have their actual measurements recorded at each subsequent evaluation, even when very small (e.g., 2 mm). However, sometimes lesions or lymph nodes that are recorded as target lesions at baseline become so faint on CT scan that the radiologist may not feel comfortable assigning an exact measure and may report them as being too small to measure. When this occurs, it is important that a value be recorded on the CRF as follows:

- If it is the opinion of the radiologist that the lesion has likely disappeared, the measurement should be recorded as 0 mm.
- If the lesion is believed to be present and is faintly seen but too small to measure, a default value of 5 mm should be assigned and BML (below measurable limit) should be ticked.

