The appearance of new malignant lesions denotes disease progression; therefore, some comments on detection of new lesions are important. There are no specific criteria for the identification of new radiographic lesions; however, the finding of a new lesion should be unequivocal, that is, not attributable to differences in scanning technique, change in imaging modality, or findings thought to represent something other than tumor (for example, some “new” bone lesions may be simply healing or flare of pre-existing lesions). This is particularly important when the patient’s baseline lesions

show partial or complete response. For example, necrosis of a liver lesion may be reported on a CT scan report as a “new” cystic lesion, which it is not.

A lesion identified during the study in an anatomical location that was not scanned at baseline is considered a new lesion and will indicate disease progression.

If a new lesion is equivocal, for example because of its small size, continued therapy and follow-up evaluation will clarify if it represents truly new disease. If repeat scans confirm there is definitely a new lesion, then progression should be declared using the date of the initial scan.

V. Evaluation of Response

A. Timepoint Response (Overall Response)

It is assumed that at each protocol-specified timepoint, a response assessment occurs. Table 1 provides a summary of the overall response status calculation at each timepoint for patients who have measurable disease at baseline.

When patients have non-measurable (therefore non-target) disease only, Table 2 is to be used.

Table 1.

Timepoint Response : Patients with Target Lesions (with or without Non-Target Lesions)

Target Lesions	Non-Target Lesions	New Lesions	Overall Response
CR	CR	No	CR
CR	Non-CR/non-PD	No	PR
CR	Not evaluated	No	PR
PR	Non-PD or not all evaluated	No	PR
SD	Non-PD or not all evaluated	No	SD
Not all evaluated	Non-PD	No	NE
PD	Any	Yes or no	PD
Any	PD	Yes or no	PD
Any	Any	Yes	PD

CR=complete response; NE = not evaluable; PD=progressive disease; PR=partial response;
SD=stable disease.

Table 2. Timepoint Response: Patients with Non-Target Lesions Only

Non-Target Lesions	New Lesions	Overall Response
CR	No	CR
Non-CR/non-PD	No	Non-CR/non-PD ^a
Not all evaluated	No	NE
Unequivocal PD	Yes or no	PD
Any	Yes	PD

CR = complete response; NE = not evaluable; PD = progressive disease.

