^a “Non-CR/non-PD” is preferred over “stable disease” for non-target disease since stable disease is increasingly used as an endpoint for assessment of efficacy in some trials; thus, assigning “stable disease” when no lesions can be measured is not advised.

B. Missing Assessments and Not-Evaluable Designation

When no imaging/measurement is done at all at a particular timepoint, the patient is not evaluable at that timepoint. If only a subset of lesion measurements are made at an assessment, usually the case is also considered not evaluable at that timepoint, unless a convincing argument can be made that the contribution of the individual missing lesion(s) would not change the assigned timepoint response. This would be most likely to happen in the case of PD. For example, if a patient had a baseline sum of 50 mm with three measured lesions and, during the study, only two lesions were assessed, but those gave a sum of 80 mm; the patient will have achieved PD status, regardless of the contribution of the missing lesion.

If one or more target lesions were not assessed either because the scan was not done or the scan could not be assessed because of poor image quality or obstructed view, the response for target lesions should be “unable to assess” since the patient is not evaluable. Similarly, if one or more non-target lesions are not assessed, the response for non-target lesions should be “unable to assess” except where there is clear progression. Overall response would be “unable to assess” if either the target response or the non-target response is “unable to assess,” except where this is clear evidence of progression as this equates with the case being not evaluable at that timepoint.

Table 3. Best Overall Response When Confirmation Is Required

Overall Response at First Timepoint	Overall Response at Subsequent Timepoint	Best Overall Response
CR	CR	CR
CR	PR	SD, PD, or PR ^a
CR	SD	SD, provided minimum duration for SD was met; otherwise, PD
CR	PD	SD, provided minimum duration for SD was met; otherwise, PD
CR	NE	SD, provided minimum duration for SD was met; otherwise, NE
PR	CR	PR
PR	PR	PR
PR	SD	SD
PR	PD	SD, provided minimum duration for SD was met; otherwise, PD
PR	NE	SD, provided minimum duration for SD was met; otherwise, NE
NE	NE	NE

CR = complete response; NE = not evaluable; PD = progressive disease; PR = partial response;
 SD = stable disease.

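### Local therapy to a target lesion is permitted on study, but the response rules do not exclude the resulting shrinkage from counting as a drug response

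*Combined protocol and SAP*

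**What the plan says.** Section 9.3 lists among permitted treatments that "Local therapy (palliative radiotherapy, surgery, radiofrequency ablation) is allowed", and Table 7 repeats it. A note in the same section describes acceptable local treatment as being of isolated lesions with palliative intent. Neither place treats target lesions differently from other lesions.

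Section 12.2 makes Appendix 4 the RECIST 1.1 criterion for this trial. There, PR is "at least a 30% decrease in the sum of diameters of target lesions, taking as reference the baseline sum of diameters", and "all lesions (nodal and non-nodal) recorded at baseline should have their actual measurements recorded at each subsequent evaluation". For lesions that become too faint to measure on CT, the appendix adds: "If it is the opinion of the radiologist that the lesion has likely disappeared, the measurement should be recorded as 0 mm". Section 12.3 requires a repeat assessment at least 4 weeks later to confirm a response.

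The only clause in Appendix 4 on locally treated lesions stands under measurability at baseline and concerns areas treated previously. It ends: "Study protocols should detail the conditions under which such lesions would be considered measurable". The protocol gives no such conditions. On incomplete assessments, Appendix 4 says: "If only a subset of lesion measurements are made at an assessment, usually the case is also considered not evaluable at that timepoint". Its Table 1 scores a target set that is not fully evaluated, without progression, as not evaluable (NE).

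Sections 12 and 14 and Appendix 5 (irRECIST) contain no rule for a target lesion treated locally on study. Section 14.2 calls the therapy promising at 4 or more responses in 27 and opens stage 2 at 1 or more in 13.

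**The concern.** The primary endpoint is meant to measure what durvalumab plus tremelimumab does to the tumor. If radiotherapy or ablation shrinks a target lesion, the sum of diameters falls, and nothing in the text removes that fall from the response calculation. Confirmation gives little protection, because a lesion reduced by local therapy may well still be small at the next scan.

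The exposure does not end with study drug. Under 14.2, patients who stop for toxicity are still followed for response under Appendix 2, which lists palliative radiotherapy as clinically indicated.

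At stake is a decision that turns on single patients. If the rule is left until such a case appears, it will be chosen with the result in view.

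**Working it through.** **1. The design as planned.** Inputs from 14.2 and 4.2: n1 = 13, stop at 0 responses; N = 27, promising at 4 or more; null rate 5%, target rate 20%. The probability of declaring the therapy promising at rate p is the sum over x = 1 to 13 of P(Bin(13, p) = x) × P(Bin(14, p) ≥ 4 − x).
- p = 0.05: 0.0416 (probability of stopping after stage 1: 0.95^13 = 0.513).
- p = 0.20: 0.8011.

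Both agree with the stated 5% and 80%.

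**2. A still-measurable irradiated lesion (hypothetical).** Target lesions of 60 and 30 mm give a baseline sum of 90. The 60 mm lesion is irradiated and measures 30 mm; the other stays at 30 mm. The change is (30 + 30)/90 − 1 = −33%, which is PR. The same sizes at the next scan confirm it. The untreated lesion has not changed: 30/30 − 1 = 0%. Every lesion was measured, so the NE wording does not apply.

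**3. How narrow the route is.** The target sum must fall to 70% of baseline or less.
- A lesion that disappears, others unchanged: its share must be at least 1 − 0.70 = 30%.
- A lesion that disappears, others growing 10%: at least 1 − 0.70/1.10 = 36%.
- A lesion that halves, others unchanged: at least 0.30/0.50 = 60%. In step 2 the share is 60/90 = 67%.
- In step 2 the sum may not exceed 0.70 × 90 = 63 mm, so the untreated lesion can reach at most 33 mm (+10%).

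There must also be no new lesion and no non-target progression through confirmation.

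**4. Effect on the denominator.** Under 14.2 a treated patient with a baseline and one post-baseline assessment is response-evaluable. NE applies to a timepoint and does not remove the patient. The practical contrast is therefore responder versus non-responder among the same 27.

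**5. Effect on type I error.** Let m be the share of true non-responders scored as confirmed PR because of local therapy. The documents give no value, so m is an assumption. The effective rate at the null is 0.05 + 0.95m, entered in the formula of step 1.

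| m | effective rate | type I error |
|---|---|---|
| 0 | 0.0500 | 0.042 |
| 0.1% | 0.0510 | 0.044 |
| 0.25% | 0.0524 | 0.048 |
| 1% | 0.0595 | 0.070 |
| 2% | 0.0690 | 0.107 |

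The 5% limit is passed at an effective rate of 0.0531, that is m = (0.0531 − 0.05)/0.95, about 0.33%. The probability of stopping after stage 1 at the null falls from 0.513 to 0.395 at m = 2%.

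**6. Cost of a stricter rule.** If true responses are lost so that the effective rate falls from 20% to 19.75% or 19.5% (assumptions), power falls from 0.801 to 0.792 or 0.784.

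**The case against.** A reader might infer that surgery is the clearest case. With targets of 40 and 50 mm, the first resected and entered at 0 mm and the second growing to 52 mm, the change is 52/90 − 1 = −42%, an apparent PR. The documents do not support that cleanly. The 0 mm instruction is written for lesions that fade on CT, not for lesions that have been removed. The sentence on incomplete measurement fits a resected lesion better and points to NE at that timepoint. The text does not settle it, but resection is the weaker case. Nor does Appendix 4 offer the alternative of scoring such a patient as stable disease on the untreated lesion alone; that would be a new rule.

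A reader might also take the error rate to be about 13%. Given one false response at a true 5% rate, the chance of declaring the therapy promising is 0.139 if it falls in stage 1, P(Bin(26, 0.05) ≥ 3), or 0.126 if it falls in stage 2. Those figures assume that the event has happened, and they would be the same for a false response from any cause. They are not the operating characteristic of this plan.

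The rest of the opposing case is fair on size. Local treatment is described as palliative and for isolated lesions, and the conditions in step 3 are demanding. At the two smaller assumed rates, type I error stays below 5%. The 0.33% threshold mainly reflects how little slack the design has (0.042 against 0.05). None of this supplies a scoring rule for an irradiated or ablated lesion that remains measurable.

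**Conclusion.** The point holds for target lesions that are irradiated or ablated on study and can still be measured: followed literally, Appendix 4 credits their shrinkage to the study drugs. For resected lesions the text leans toward NE but leaves the matter open.

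The size is unknown because the documents give no frequency. The error rates in step 5 rest on assumed misscoring rates and show sensitivity, not expected inflation. What does not depend on them is that one such response can turn 3/27 into 4/27, or take the trial past the first-stage stop. This is a worthwhile clarification of the primary endpoint. It does not call the design, the sample size or the permitted care into question.

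**What to change.** Add to 14.2, as a stated exception to Appendix 4 Table 1:

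- Shrinkage or disappearance of a target lesion after on-study local therapy to that lesion cannot contribute to CR or PR.
- A response confirmed before the date of local therapy stands.
- After that date, a PR counts only if the untreated target lesions alone meet the criterion against their own baseline sum.
- Progression is judged on the untreated target lesions against their own nadir, together with non-target and new lesions.
- Patients without a response under this rule remain in the evaluable population as non-responders.

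Apply the same rule to the clinical benefit rate and to the irRECIST response endpoints. Record the lesion and the date of any local therapy. Concomitant treatment is already collected, and Appendices 2 and 3 list palliative radiotherapy in follow-up, but none of these asks which lesion was treated. What local therapy is allowed does not change.

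The cost is a few sentences, one data field and an occasional true response lost, for example when the only target lesion is treated before confirmation. Power could then fall slightly below 80% (step 6). At very small rates the numerical trade is about even or slightly unfavorable: losing 0.25 percentage points of response costs about 0.009 of power (0.8011 − 0.7925), while preventing 0.25% misscoring saves about 0.006 of type I error (0.0480 − 0.0416). The stronger reason for the rule is that it is fixed before any response is read.
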